1. STUDY TEAM

Partner Institutions: Guangdong Provincial Center for Skin Diseases and STI Control, University of North Carolina at Chapel Hill, University of California San Francisco, London School of Hygiene and Tropical Medicine, Shandong University, Shandong Provincial Centers for Disease Control and Prevention

PIs: [name], [name]

Survey development: [name], [name], [name], [name], [name],

[name], [name]

Statisticians: [name], [name], [name], [name]

Crowdsourcing Intervention Arm: [name], [name], [name], [name], [name] Social Marketing Intervention Arm: [name], [name], [name], [name], [name]

Costing Analysis: [name], [name], [name], [name] MSM recruitment: [name], [name], [name] Oversight: [name], [name], [name], [name]

Funding support: National Institutes of Health (NIAID 1R01AI114310-01), UNC-South China STD Research Training Center (FIC 1D43TW009532-01), UNC Center for AIDS Research (NIAID 5P30AI050410-13), UCSF Center for AIDS Research (NIAID P30 AI027763), NIMH (R00MH093201), UJMT Fogarty Fellowship (FIC R25TW0093), and SESH Global (www.seshglobal.org). Administrative assistance from the Guangdong Provincial Center for Skin Diseases and STI Control. UNC Chapel Hill, ProofPilot, and UNC Project-China in Guangzhou, China.

2. SUMMARY

Crowdsourcing may be a powerful tool to spur the development of innovative videos to promote condom use among key populations such as men who have sex with men (MSM) and transgender individuals (TG). The purpose of this randomized controlled trial is to compare the effect of a crowdsourced video and a social marketing video on condom use among Chinese MSM and TG who report condomless anal/vaginal sex during the past three months. The crowdsourced video was developed using an open contest, formal transparent judging, and several prizes. The hypothesis is that a crowdsourced video will not be inferior (within a margin

of 10%) to a social marketing video in terms of reported condomless sex after three to four weeks (with an additional follow-up at three months) following the one-time video watching.

3. BACKGROUND

Although male condoms have long been recognized as an effective method for reducing the risk of HIV and other sexually transmitted diseases (STDs)^{1,2}, men who have sex with men (MSM) practice inconsistent condom use in China.³⁻⁶ The resulting high incidence of HIV and STDs among MSM suggests the need for novel health promotion campaigns. One systematic review⁷ and one literature review among MSM⁸ demonstrate that social marketing campaigns are effective in promoting condom use, but the persistence of these behavioral changes over time is unclear. Community engagement in these campaigns is also variable. We propose that crowdsourcing may substantially improve on existing methods for developing condom promotion campaigns. Crowdsourcing is the process of taking a task performed by an individual and outsourcing it to a large group in the form of a contest or open call, often enabled by the Internet.⁹ Crowdsourcing has been used extensively in the private sector and championed by the Executive Office of the President of the United States as a cost-effective tool to generate creative, new ideas.¹⁰ Similarly, crowdsourcing can be applied to enhance condom promotion and linkage programs by generating diverse ideas and increasing key population engagement.

A crowdsourced approach to promoting condom use substantially differs from social marketing approaches in three ways. First and foremost, crowdsourced campaigns are developed "bottomup" based on crowd input while social marketing campaigns are "top-down" and often rely on public health expert opinions. Second, crowdsourced campaigns increase community

engagement from idea generation to implementation while social marketing approaches have limited community engagement. Third, crowdsourced campaigns have a high potential for innovation compared to social marketing approaches. Cognitive psychology and creativity research show how conventional approaches to the design and implementation of sexual health education programs may stifle creativity. This literature suggests that past experience is detrimental to future ideation efforts.¹¹ Experimental research demonstrates that cognitive fixation is a pervasive impediment to developing novel ideas.¹²⁻¹⁶ People gravitate towards ideas that bear structural and technical resemblance to prior examples,^{14,17} resulting in less creative ideas. Our team has used crowdsourcing to develop an effective HIV testing promotion video¹⁸ and images promoting sexual health.¹⁹

4. SPECIFIC AIMS AND HYPOTHESES

Specific Aim 1: To compare the effect of a crowdsourced one-minute video to a social marketing one-minute video in promoting condom use among MSM and TG in China. This includes data at 3 weeks post-video and data from 3 months post-video.

Hypothesis 1: Crowdsourced videos are not inferior to social marketing videos to promote condom use among MSM and TG in China.

Specific Aim 2: To compare the cost of using crowdsourcing compared to social marketing methods for developing short videos focused on promoting condom use among MSM and TG individuals in China.

Hypothesis 2: A crowdsourced video is cost saving compared to a social marketing video for promoting condom use.

Specific Aim 3: To compare the effect of a crowdsourced one-minute video to a social marketing one-minute video in changing condom use self-efficacy among MSM and TG individuals in China.

Hypothesis 3: Crowdsourced videos are not inferior to social marketing videos in changing condom use self-efficacy among MSM and TG in China.

5. STUDY DESIGN

Formative work: Two trained study team members will conduct interviews with MSM and stakeholders in order to inform development of the online survey. We will interview key informants specifically about conducting an Internet survey among MSM in China. We will partner with the community-based organization responsible for the largest MSM web portal in China (www.danlan.com). This MSM web platforms provide a structured mechanism for social networking, meeting friends, exchanging news and information, and banner advertising (Appendix 1). We will pilot the survey online with approximately 100 volunteer MSM. The purpose of the pilot study will be to gauge post-intervention condom usage rates and to estimate the necessary sample size for the non-inferiority study. We will also conduct semi-structured interviews to solicit feedback on question wording and interpretation. Pilot data will not be included in the final analysis. The purpose of this extensive formative research is to ensure that the online survey is simple and easy to complete. The CONSORT-Ehealth checklist for online surveys²⁰ will be used to ensure completeness.

Study Design: This study will be a pragmatic, non-inferiority, randomized controlled trial comparing two groups – men who watch a crowdsourced video and men who watch a social marketing video.

Main and Secondary Outcomes: The main outcome of this study will be any condomless anal or vaginal sex with any sex partner at three weeks and three months following the video. Individuals who do not reply to the three week message will receive a second message at four weeks. Secondary outcomes include cost, self-efficacy, and other behavioral variables (Appendix 2).

Eligibility and Recruitment: Participants will be recruited through a banner link on a popular MSM web portal home page and an announcement sent to registered users by email and other social media platforms. Interested participants who click on the link will then be directed to the survey with a description of its contents and an online informed consent form. The survey is voluntary and to be eligible, participants must state that they were born biologically male or are transgender, had anal sex with men at least once during their lifetime, have had condomless anal/vaginal sex in the past three months, and are at least 16 years of age. All participants must provide their cell mobile number. Individuals identified by their cell phone number who enter the study twice and watch different videos will be excluded. No names or addresses will be collected from participants. All individuals who enroll in the study and reply to the text message will receive a 100 RMB (8.50 USD) pre-paid cell phone card for their time at the first FU and a 50 RMB pre-paid card for the second FU.

Measures: Survey items on socio-demographics and sexual behaviors will be collected using standardized survey instruments immediately before video watching, three weeks after video watching, and three months after video watching. Socio-demographic characteristics include participants' age, highest level of education completed, annual income, marital status, sexual orientation, and sexual orientation disclosure. Behavioral variables include number of sex acts in the past three weeks, condomless sex with men, condomless sex with women, condom self-efficacy, and other secondary outcomes specified in Appendix 2.

Statistical Analysis: The primary outcome will be condomless vaginal or anal sex (with any sex partner) among MSM and transgender individuals following the assigned video intervention. Participants will be asked about using condoms all the time or not using condoms all the time since watching the video (individuals who have not had sex in the interval will be classified as no condomless sex). Condomless vaginal or anal sex includes condomless sex of any frequency (e.g., always condomless sex, occasional condomless sex, etc.). We will examine the non-inferiority hypothesis comparing the two interventions, as well as the superiority hypothesis. The difference in proportions having condomless sex (crowdsourced – social marketing) will be estimated, with a corresponding two-sided 95% Wald confidence interval. The crowdsourced intervention will be declared non-inferior to social marketing if the upper confidence limit is below 10%. If the upper confidence bound is below 0%, then the crowdsourced intervention will be declared superior to social marketing.

Our secondary outcomes are condom use self-efficacy, cost, and related behavioral outcomes. The objective of the cost analysis will be to estimate the total and incremental unit cost in using

video interventions to promote condom use. In this step, we will further collect cost related data from all the organizations involved in making condom use promotion videos. Detailed information that we will collect from these organizations is listed in Appendix 2. One of our secondary analyses will focus on those individuals who reported sex following the video intervention (excluding those who did not have sex in the interval between the video and the survey).

Missing Data Plan: Missing data in the primary outcome that accounts for <11% of participants will not be imputed and the complete-case approach will be used. However, in cases where missing data for the primary outcome is 11 to <20% of the total outcome, a sensitivity analysis using multiple imputation based on the PROC MI procedure in SAS (Cary, NC) will be used. If missing data accounts for \geq 20% of participants then we will use multiple imputation in the primary analysis.

Effect modification analyses: Effect modification analyses will be undertaken based on prior exposure to condom promotion video watching to assess whether this exposure differs between the baseline groups. A linear probability model will be used to evaluate effect modification by testing for an interaction between intervention and prior video watching (e.g.,

 $Prob(Condomless Sex = 1 | Arm, AgeGrp) = \alpha + \beta_1 Arm + \beta_2 AgeGrp + \beta_3 Arm * AgeGrp).$ This model can be fit with the GENMOD procedure in SAS using the binomial distribution and identity link. If this model does not converge, then log-binomial regression will be used to estimate relative risks. *Secondary analysis:* We will examine the subset of individuals who reported sex during the follow-up period (3 weeks and 3 months respectively) and use causal inference methods to account for post-randomization selection bias. We will compare the proportion of individuals who have any sex between the two arms to determine if the intervention results in less frequent sex.

Sample size calculation: To calculate sample size we assumed an equal probability of reported condomless sex in the crowdsourced video intervention and social marketing intervention arms. We calculated the sample size for this binary outcome non-inferiority trial using the formula below with a one-sided significance level (α) of 2.5% and power (1- β) of 90%.²¹ Assuming a 50% probability of condomless sex in each arm, a non-inferiority limit of 10%, and loss to follow-up of 10%, a total sample size of 1170 individuals is required (585 in each arm). The sample size calculation was made using the formula:

$$n = f(\alpha, \beta) \frac{[\pi_s (1 - \pi_s) + \pi_e (1 - \pi_e)]}{(\pi_s - \pi_e - d)^2}$$

where π_s and π_e are the true probability of reported condomless sex in the social marketing intervention and crowdsourced video (experimental) intervention groups, respectively, d is the non-inferiority limit, and $f(\alpha, \beta) = [\Phi^{-1}(\alpha) + \Phi^{-1}(\beta)]^2$, where Φ^{-1} represents the cumulative distribution function of the standard normal distribution.

Sample size calculations for 90% power and a one-sided 0.025 significance level

| Probability | Probability | Non- | Probability of | Ν | Total |
|-------------|-------------|------------|-----------------------|---------|----------|
| of primary | of primary | inferiorit | loss to follow- | evaluab | sample |
| outcome in | outcome in | y limit | up £ | le per | size for |

| control group [*] | experimenta l group [*] | | | arm | RCT |
|-------------------------------|-------------------------------------|-----|-----|-----|------|
| 0.50 | 0.50 | 0.1 | 0.1 | 526 | 1170 |
| 0.45 | 0.45 | 0.1 | 0.1 | 521 | 1158 |
| 0.40 | 0.40 | 0.1 | 0.1 | 505 | 1122 |
| 0.35 | 0.35 | 0.1 | 0.1 | 479 | 1064 |
| 0.30 | 0.30 | 0.1 | 0.1 | 442 | 982 |

Note: *Based on the pilot study, 9/25 (95% confidence interval: 18% to 57%) had condomless sex at least once in the three week period immediately following the video intervention. \pounds According to one similar RCT we conducted at 2014, the lost to follow up rate was about 10%; adjustment for loss: required evaluable N per arm/(1-loss to follow up).

Ethical review: IRB approval will obtained from the following institutional ethical review boards

prior to study enrollment - Guangdong Provincial Center for Skin Diseases and STI Control,

University of North Carolina at Chapel Hill, and University of California San Francisco.

Trial registration: This trial was registered in ClinicalTrials.gov (NCT02516930).

References

3. Ministry of Health People's Republic of China. 2012 China AIDS Response Progress Report. Beijing2012.

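### The protocol contradicts itself on which time point decides non-inferiority; unless three weeks alone is primary, the stated 2.5% error and 90% power do not both hold for an overall claim

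*Protocol*

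**What the plan says.** The protocol describes the timing of the primary comparison in five places, and they do not agree.

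- **Summary (Section 2).** Non-inferiority within 10% is hypothesised "in terms of reported condomless sex after three to four weeks (with an additional follow-up at three months"). Three months is an extra.
- **Specific Aim 1 (Section 4).** Both times are included and neither is ranked: "This includes data at 3 weeks post-video and data from 3 months post-video".
- **Section 5, Main and Secondary Outcomes.** The main outcome is "any condomless anal or vaginal sex with any sex partner at three weeks and three months following the video". Both times have the same standing. The secondary outcomes named there are cost, self-efficacy and other behavioural variables; three months is not among them.
- **Section 5, Statistical Analysis.** The primary outcome is restated as condomless sex "among MSM and transgender individuals following the assigned video intervention", with no time point. One rule follows: "The crowdsourced intervention will be declared non-inferior to social marketing if the upper confidence limit is below 10" per cent.
- **Section 5, Sample size calculation.** One comparison is sized, at "a one-sided significance level (α) of 2.5% and power (1- β) of 90" per cent. The pilot rate in the table note (9/25) covers the three-week period only.

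Nowhere does the protocol say whether three weeks, three months, either or both must meet the rule. It gives no testing order and no division of the error rate.

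**The concern.** In a non-inferiority trial the primary time point is part of the claim. Here two time points share the label of main outcome, but there is one decision rule and one sample size. If the results at three weeks and three months disagree, the Summary and Section 5 can support opposite conclusions from the same data.

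The operating characteristics also depend on the reading. Two chances to succeed raise the probability of a false non-inferiority claim. Two hurdles that must both be cleared lower the probability of success. The protocol states its error and power as if there were one test.

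**Working it through.** **Inputs from Section 5:** risk 0.50 in each arm, margin d = 0.10, one-sided α = 0.025, power 0.90, loss 10%. **Assumed, because the protocol does not give them:** the same risk and the same evaluable number at both times, and a correlation ρ between the two test statistics, varied from 0 to 0.9.

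**1. Reproduce the plan's figure.**
- f = (1.960 + 1.2816)² = 10.507
- n = 10.507 × (0.25 + 0.25) / 0.10² = 525.4, so 526 evaluable per arm
- 526 / 0.90 = 584.4, so 585 per arm and 1170 in total

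This matches the protocol. Power with 526 per arm: the standard error is √(2 × 0.25 / 526) = 0.03083, so 0.10 / 0.03083 − 1.960 = 1.2835, and Φ(1.2835) = 90.0%. This is the power of one comparison.

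**2. Two time points.** Let Φ₂(a, b; ρ) be the standard bivariate normal distribution function.
- Error if either time suffices, with the true difference at the margin at both times: 1 − Φ₂(1.960, 1.960; ρ)
- Power if both are required, with no true difference at either time: Φ₂(1.2835, 1.2835; ρ)

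| ρ (assumed) | One-sided error, either time | Power, both times |
|---|---|---|
| 0 | 4.9% | 81.1% |
| 0.5 | 4.5% | 83.3% |
| 0.8 | 3.9% | 85.7% |
| 0.9 | 3.5% | 86.9% |

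Requiring both keeps the error at or below 2.5%. Accepting either does not reduce power: the chance of at least one success is 99% at ρ = 0 and 93% at ρ = 0.9.

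**3. Where ρ is likely to lie.** The Statistical Analysis paragraph asks about condom use since watching the video. If that wording applies at both follow-ups and answers are consistent, everyone with the outcome at three weeks also has it at three months. For such nested outcomes with risks p₁ ≤ p₂, ρ = p₁(1 − p₂) / √[p₁(1 − p₁) p₂(1 − p₂)]. Take the pilot's 36% at three weeks and an assumed 50% at three months:
- ρ = 0.36 × 0.50 / (0.48 × 0.50) = 0.75
- error if either suffices: about 4.0%
- power if both are required: about 87%, from single-test powers of 92.2% and 90.0%

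Values of ρ towards the upper end of the range are therefore the more plausible, and the departure is then smaller, but it remains.

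**4. What equal standing would cost.**
- Splitting α to 0.0125 at each time: n = (2.2414 + 1.2816)² × 0.5 / 0.01 = 620.6, so 621 evaluable per arm. Then 621 / 0.90 = 690 per arm, 1380 in total, for 90% power at each time.
- 90% power to succeed at both times: 646 evaluable per arm at ρ = 0 (1436 in total), falling to 578 at ρ = 0.9 (1286 in total).

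**The case against.** The best defence is that the protocol leans towards three weeks. The Summary states the hypothesis there, the second message at four weeks is described only for that follow-up, the pilot window is three weeks, and the first follow-up carries the larger payment. On that reading 2.5% and 90% both hold with 1170 participants. A second defence is that the two times could yield separate conclusions with no combined claim, as the analysis of sexually active participants seems to treat them. Each test would then keep its own error, and its own power at 10% loss. A third is that testing order often belongs in a statistical analysis plan, which is not shown here.

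These points limit the consequence but leave the contradiction in place. The sentence that defines the main outcome names both times, and an analysis plan would have to override either that sentence or the Summary.

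Three stronger readings are tempting, and the documents do not support them:
- **That the stated error and power simply fail.** They hold if three weeks alone is primary, and no reading breaks both: accepting either time raises error without lowering power, and requiring both lowers power without raising error.
- **That heavier loss at three months cuts power further.** The only loss rate given is about 10%, and no separate rate is stated for three months. At 20% or more missing, the plan moves its primary analysis to multiple imputation, so a complete-case power figure at that loss would not describe the planned analysis.
- **That the sample size rests on the pilot's three-week rate.** It uses 50%, where the variance is largest, so a single test at any other common risk has at least the stated power at the same retention.

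Testing superiority on the same interval after non-inferiority adds no error and is not part of this point.

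**Conclusion.** The point stands as an internal contradiction with conditional consequences. The protocol does not settle which time point, or which combination, decides non-inferiority. Its sample size supports one comparison. For an overall claim resting on both times, one of the two stated figures is lost: the error becomes about 3.5% to 4.9% if either time suffices, or power becomes about 81% to 87% if both are required. These ranges rest on 50% risk and 526 evaluable per arm at both times, and on an assumed correlation of 0 to 0.9. The true value is probably towards the upper end, where the loss is smallest. The direction does not depend on the exact correlation within that range. A reader should not infer that the trial is undersized or its error rate wrong under the Summary's hypothesis; there, both figures are correct.

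**What to change.** In Section 5, under both the main outcome and the decision rule:

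1. Name condomless sex at the three-week follow-up, including replies to the four-week reminder, as the single primary outcome. This agrees with the Summary and the pilot window.
2. Make condomless sex at three months a key secondary outcome, tested for non-inferiority at one-sided 2.5% only if three-week non-inferiority has been shown. The fixed order keeps the overall one-sided error for the two non-inferiority claims at 2.5%.
3. State that the 90% power applies to the three-week comparison.
4. Align the wording of Specific Aim 1.

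This changes wording only, and the total stays at 1170. The cost is that the three-month claim becomes conditional on the three-week result. If the sponsor wants the two times to stand equally, the protocol should say whether either or both must succeed, and the trial should be resized accordingly: 1380 in total with a split error rate, or about 1286 to 1436 if both are required, under the assumptions above.

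### People who enter twice and watch both videos are dropped after randomisation, with no analysis by first assignment, which can bias the primary difference if re-entry depends on the first video

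*Protocol*

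**What the plan says.** Section 5 of the protocol, under Eligibility and Recruitment, makes the phone number compulsory ("All participants must provide their cell mobile number") and then states: "Individuals identified by their cell phone number who enter the study twice and watch different videos will be excluded". No names or addresses are collected, so the number is the only stated means of recognising a repeat entrant. Replies are paid: "All individuals who enroll in the study and reply to the text message will receive a 100 RMB (8.50 USD) pre-paid cell phone card" at the first follow-up, and a 50 RMB card at the second.

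The Study Design paragraph describes the trial as "comparing two groups – men who watch a crowdsourced video and men who watch a social marketing video". The Statistical Analysis paragraph defines the primary outcome "among MSM and transgender individuals following the assigned video intervention". Non-inferiority is declared if the upper limit of the two-sided 95% Wald interval for crowdsourced minus social marketing is below 10%.

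The protocol does not say that a known number is blocked or sent back to its first video. It does not place excluded people under their first assignment in any analysis, and it gives no expected number of repeat entrants.

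**The concern.** The rule sits among the eligibility criteria but cannot work as one. Whether it applies is known only after a person has been allocated, has watched a video, has come back and has watched a different one. It is therefore a post-randomisation exclusion that depends on the videos drawn, and it removes people who already have an assigned video from a comparison defined by the assigned video.

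Re-entry follows the first viewing, so the first video could in principle influence who comes back. If it does, and those who come back have a different risk of condomless sex, the exclusion removes a different slice of risk from each arm. The non-inferiority conclusion depends on the distance from the upper confidence limit to the margin, so a shift of a point or two could matter in a close result. The protocol takes this kind of selection seriously elsewhere: for the subset who had sex during follow-up it plans causal methods to deal with selection after randomisation. It states no such protection for the primary comparison.

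**Working it through.** **Inputs from the protocol (section 5, sample size and statistical analysis):** 50% risk in each arm, margin d = 10 points, one-sided α = 2.5%, power 90%, 10% loss to follow-up, 585 per arm.

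**1. The plan's own sample size.** f(α, β) = (1.960 + 1.282)² ≈ 10.51. n = 10.51 × (0.25 + 0.25) / 0.10² ≈ 525.4, so 526 evaluable per arm. 526 / 0.9 = 584.4, so 585 per arm and 1170 in total. This reproduces the plan.

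**2. Room to the margin.** The 95% half-width at 526 per arm is 1.96 × √(0.5/526) = 6.0 points. At zero observed difference, 10 − 6.0 = 4.0 points remain.

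**3. Effect of the rule on one arm.** Assumptions, none of them given in the protocol:
- A fraction r of the arm re-enters.
- The second draw is independent and 1:1, so half of the re-entrants see the other video and are removed.
- Re-entrants have risk 0.5 + δ.
- The arm's total risk is held at 0.5, so there is no true effect.

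After the exclusion the arm's risk is

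[0.5 − (r/2)(0.5 + δ)] / (1 − r/2) = 0.5 − (rδ/2) / (1 − r/2).

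The bias is the crowdsourced shift minus the social marketing shift. If r and δ are the same in both arms, it is exactly zero.

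Example with r = 10% (crowdsourced) against 2% (social marketing) and δ = 0.40: the shifts are −0.020/0.95 = −2.11 points and −0.004/0.99 = −0.40 points, so the bias is −1.70 points.

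**4. Scenarios (bias in percentage points; negative favours the crowdsourced video).**

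| Re-entry, crowdsourced vs social marketing | δ = +20 points | δ = +40 points |
|---|---|---|
| Equal (2%, 5% or 10% in both) | 0.00 | 0.00 |
| 5% vs 2% | −0.31 | −0.62 |
| 10% vs 5% | −0.54 | −1.08 |
| 10% vs 2% | −0.85 | −1.70 |
| 15% vs 5% | −1.11 | −2.22 |
| 2% vs 10% | +0.85 | +1.70 |

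A simulation of 4 million entrants agreed within noise. For 10% vs 2% and δ = +40 points it gave −1.60 points with the exclusion and +0.09 when everyone was kept under first assignment. For 10% vs 5% and δ = +20 points it gave −0.55 and −0.01.

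**5. Against the room.** 0.3/4.0 ≈ 8% and 2.2/4.0 = 55% of the distance to the margin at zero observed difference.

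**6. Numbers lost and power.** At 5% re-entry in both arms, 0.05 × 1170 / 2 ≈ 29 people are removed. Evaluable n per arm = 585 × (1 − r/2) × 0.9, and power = Φ(0.10/√(0.5/n) − 1.96):

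| Re-entry | n per arm | Power |
|---|---|---|
| 0% | 526.5 | 0.9006 |
| 2% | 521.2 | 0.8977 |
| 5% | 513.3 | 0.8933 |
| 10% | 500.2 | 0.8855 |

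**The case against.** The strongest reply is that the rule treats the arms alike. With a 1:1 second draw, a re-entrant is removed with probability one half whichever video came first, so dependence on the second draw alone produces no bias. Bias needs both arm-dependent re-entry and re-entrants at different risk, and the protocol gives no evidence of either. The one documented reason to come back, the phone card for replying, is the same in both arms. This stands, and it limits the point to a possible bias.

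It can also be said that people who saw both videos are contaminated. Keeping them pulls the arms together, which in a non-inferiority trial can help the claim, so dropping them is a recognisable per-protocol choice. That also stands. It supports the exclusion as a companion analysis, but not as the only stated handling.

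Two stronger readings are tempting and not supported. A reader might infer that the rule breaks the randomised comparison; step 3 of the working shows that it does not when re-entry and excess risk are equal by arm. A reader might also infer that people who draw the same video twice stay in as two non-independent records. The protocol is silent on same-video repeats, and de-duplication may be settled in an analysis plan that is not shown, so that inference is not part of this point.

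An unseen analysis plan could add an analysis by first assignment. The protocol nevertheless states the exclusion without qualification, and preventing a second allocation is a matter for the enrolment platform that no analysis plan can repair afterwards.

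**Conclusion.** The point holds as a risk of bias, not as a demonstrated one. The protocol fixes a post-randomisation exclusion that depends on the videos drawn, sets it beside a primary comparison by assigned video, and states no analysis by first assignment for those removed.

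The bias is zero if re-entry and the excess risk of re-entrants are equal in both arms. Under the assumed unequal rates it is about 0.3 to 2.2 points in either direction, against about 4.0 points of room at zero observed difference. The upper end needs frequent and clearly unequal re-entry together with a 40-point excess risk. All re-entry rates and risks are assumptions, as are the independent 1:1 second draw and the absence of a true effect. The loss of power is negligible. The likely effect is small, and the change is worth making mainly because it is cheap.

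**What to change.** Collect the mobile number before allocation and check it against numbers already enrolled. Return a repeat number to its original video with no second randomisation. This prevents both the exclusion and the exposure to two videos.

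For repeats that slip through, state that each number is analysed once, in the arm first allocated and with the first baseline record, and report the number of repeats by first arm. Keep the present exclusion as a sensitivity (per-protocol) analysis.

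The cost is a lookup in the online platform and a sentence or two in the protocol. The protocol requires the number but does not say when it is collected, so the order of the enrolment screens may need to change. Someone who re-enters under a different number escapes both the present rule and this one. The statistical downside is that the few retained people who saw both videos slightly dilute the contrast, which can favour a non-inferiority claim. The sensitivity analysis would show whether that matters.
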